Appendix B: Acceptable Ranges of Screening Laboratory and Vital Sign Measurements

Table 4: Acceptable Ranges of Screening Laboratory and Vital Sign Measurements – Hematology and Chemistry

HEMATOLOGY AND CHEMISTRY				
Lab test name	Reference range	Acceptable lower limit	Acceptable upper limit	Lab unit
Hemoglobin (Hgb), male	13.2 - 17.1	13.0	18.5	g/dL
Hemoglobin (Hgb), female	11.7 – 15.5	11.3	16.5	g/dL
Hematocrit (Hct), male	38.5 – 50.0	38.5	54	%
Hematocrit (Hct), female	35 - 45	35	49	%
White blood cell count (WBC)	3,800 – 10,800	3,500	11,500	cells/ μ L
Neutrophil count	1,500 – 7,800	1,200	8,500	cells/ μ L
Lymphocyte count	850 – 3,900	800	5,000	cells/ μ L
Monocyte count	200 - 950	0	1,100	cells/ μ L
Eosinophil count	150 - 500	0	600	cells/ μ L
Basophil count	0-200	0	300	cells/ μ L
Platelet count	140 - 400	125	475	$10^3/\mu$ L
Sodium	135 - 146	132	148	mmol/L
Potassium	3.5 - 5.3	3.3	5.5	mmol/L
CO ₂ (Bicarbonate)	20 - 32	19	33	mmol/L
Chloride	98 -110	94	115	mmol/L
Calcium	8.6 - 10.3	8.0	11.0	mg/dL
Magnesium	1.5 - 2.5	1.1	2.8	mg/dL
Blood urea nitrogen (BUN)	7 – 25	0	28	mg/dL
Glucose, fasting	65 - 99	50	115	mg/dL
Serum creatinine, male	0.6 – 1.35	0.5	1.45	mg/dL
Serum creatinine, female	0.5 – 1.10	0.4	1.2	mg/dL
Direct bilirubin	0.0-0.2	0	0.4	mg/dL
Total bilirubin	0.2 – 1.2	0	1.4	mg/dL
Total protein	6.1 - 8.1	5.8	8.6	g/dL
Albumin	3.6 – 5.1	3.2	6.0	g/dL
Aspartate transferase (AST), male	10 - 40	0	45	U/L
Aspartate transferase (AST), female	10 - 30	0	35	U/L
Alanine transferase (ALT), male	9 - 46	0	52	U/L
Alanine transferase (ALT), female	5 - 32	0	38	U/L
Alkaline phosphatase, males	40 - 115	0	150	U/L
Alkaline phosphatase, females	33 – 115	0	150	U/L
Hepatitis B surface antigen (HBsAg)	non-reactive	non-reactive	non-reactive	n/a
Hepatitis C antibody (HCVAb)	non-reactive	non-reactive	non-reactive	n/as
HIV-1/ HIV-2 antibody	non-reactive	non-reactive	non-reactive	n/a

Serum β -HCG (females only)	negative	negative	negative	n/a
FSH (post-menopausal females only)	23 – 116.3	23	116.3	mIU/mL

Footnotes: Exceptions to screening laboratory tests' normal reference ranges are:

- a. Racially-based low total WBC or neutrophil counts up to toxicity Grade 1 in [Appendix C](#) Toxicity Tables are allowed, but toxicity Grades 2 or 3 are exclusionary.
- b. Abnormalities in mean corpuscular volume (MCV), mean corpuscular hemoglobin (MCH), mean corpuscular hemoglobin concentration (MCHC), red cell distribution width (RDW), mean platelet volume (MPV), and nucleated red blood cell count (NRBC CT), which are included in a CBC with differential, will not be exclusionary. These results will be included in the database for comparison with results obtained as a part of safety laboratory tests.
- c. Abnormalities in serum creatinine, BUN, total bilirubin, AST, ALT, and chloride below the lower limit of normal (LLN) are allowable.
- d. Elevated bilirubin due to documented Gilbert syndrome that is Grade 1 is allowable, but Grade 2 or higher is exclusionary. [To document a subject has Gilbert syndrome, a diagnosis from the medical record must will be provided or the PI may make a 'presumptive' diagnosis of Gilbert syndrome in subjects with unconjugated hyperbilirubinemia on repeated testing (at least two samples separated in time) who have otherwise normal serum ALT, AST, and AP concentrations, and a normal CBC].
- e. Elevated serum glucose, sodium, potassium, bicarbonate (CO₂), total protein, and AP values that reach toxicity Grade 1 values are allowable.
- f. Serum chloride and albumin values above the ULN are allowable.
- g. Other laboratory values that are outside the range of eligibility but are thought to be due to an acute condition or due to collection or laboratory error may be repeated once.

URINALYSIS ^a

Table 5: Acceptable Ranges of Screening Laboratory and Vital Sign Measurements – Urinalysis

Lab test name	Reference range limit	Acceptable lower limit	Acceptable upper limit	Lab unit
Urine dipstick				
Protein	negative	negative	1+ ^b	
Blood	negative	negative	trace ^b	
Glucose	negative	negative	trace ^b	
Urine Microscopy				
WBCs in urine (sediment)	0-5	0	6	/field
RBCs in urine (sediment)	0-2	0	6	/field
Bacteria	none	few	^b	/field
Hyaline casts	none	none	trace ^b	/field
Crystals	none	0	^b	
Footnotes:				
^a (1) If UA by dipstick is abnormal, a complete UA with microscopic evaluation will be performed and the results will supersede the results of the dipstick. (2) Menstruating females failing inclusion criteria due to a positive blood on a urine test (dipstick or microscopic UA) may be retested following cessation of menses. Do not exclude female subjects with ≤ 6 RBC/HPF.				
^b Per investigator judgment, based on medical history.				

TOXICOLOGY

Urine must be negative for all tested substances [amphetamines, cocaine (and metabolite), barbiturates, benzodiazepines, opiates, tetrahydrocannabinol, methamphetamines, methadone, TCA, MDMA, and phencyclidine]. Urine creatinine will be measured as part of the profile to assess quality of collected sample.

VITAL SIGNS

Table 6: Acceptable Ranges of Screening Laboratory and Vital Sign Measurements – Vital Signs

Measurement	Lower limit	Upper limit	Lab unit
Systolic BP	90	150	mmHg
Diastolic BP	40	90	mmHg
Pulse rate	45	100	bpm
Respiratory rate	8	22	breaths/min
Oral temperature	95.9 (35.5)	<100.4 (<38.0)	°F (°C)

Appendix C: Adverse Events Toxicity Grading Criteria

ABBREVIATIONS: Abbreviations utilized in the Table:

LLN = Lower Limit of Normal

Req = Required

IV = Intravenous

Dec = Decreased

ESTIMATING SEVERITY GRADE

For abnormalities NOT found elsewhere in the Toxicity Tables, use the scale below to estimate grade of severity:

GRADE 1	Mild	Events require minimal or no treatment; do not interfere with the subject's daily activities.
GRADE 2	Moderate	Events result in a low level of inconvenience or concern with therapeutic measures; may cause some interference with functioning.
GRADE 3	Severe	Events interrupt a subject's usual daily activity and may require systemic drug therapy or other treatment; are usually incapacitating.

SERIOUS OR LIFE-THREATENING AEs

Clinical events considered to be serious or life-threatening include, but are not limited to: seizures, coma, tetany, diabetic ketoacidosis, disseminated intravascular coagulation, diffuse petechiae, paralysis, acute psychosis, and severe depression.

COMMENTS REGARDING THE USE OF THESE TABLES

- Standardized and commonly used toxicity tables (Division of AIDS, National Cancer Institute [NCI] Common Toxicity Criteria [CTC], and World Health Organization [WHO]) have been adapted for use by the Division of Microbiology and Infectious Diseases (DMID) and modified to better meet the needs of subjects in DMID trials.
- For parameters not included in the following Toxicity Tables, the CTU will refer to the "Guide for Estimating Severity Grade" located above.
- Criteria are generally grouped by body system.

Some protocols may have additional protocol specific grading criteria, which will supersede the use of these tables for specified criteria.

Table 7: Toxicity Grading Tables – Clinical AEs

Toxicity Grading Tables				
Clinical AEs	Mild (Grade 1)	Moderate (Grade 2)	Severe (Grade 3)	Comments
VITAL SIGNS				
Fever - °C	38.0-38.4	38.5-38.9	>38.9	No recent hot or cold beverages or smoking. A protocol should select either °C or °F for inclusion
Fever - °F	100.4-101.1	101.2-102.0	>102.0	
Tachycardia - bpm	101-115	116-130	>130 or ventricular dysrhythmias	Assume awake and in supine position for 5 min at rest; for AE, measurements at least 3 times with 2 concordant results (Section 8.1.6)
Bradycardia – bpm • Baseline >60 OR, if • Baseline <60	• 50-54 OR, if Baseline <60, • 45-50	• 45-49 OR, if baseline <60, • 40-44	• <45 OR, if baseline <60 • <40	As above
Hypertension (systolic) - mmHg	141-150	151-160	>160	Assume awake, and in supine position for 5 min at rest; for AE, measurements on same arm at least 3 times with 2 concordant results (Section 8.1.6)
Hypertension (diastolic) - mmHg	91-95	96-100	>100	As above
Hypotension (systolic) - mmHg	85-89	80-84	<80	As above
Tachypnea – breaths per min	23-25	26-30	>30	Assume awake and in supine position for 5 min at rest; for AE, measurements at least 3 times with 2 concordant results (Section 8.1.6)

Note: Isolated/individual abnormalities of VS would not be considered toward halting criteria. Abnormalities of VS will be described as “increased X” or “decreased X” (X = HR, BP, RR, temperature) if asymptomatic, transient and not associated with a systemic or organ-specific disorder and coded by MedDRA within the System Organ Class (SOC) “Investigations.” These abnormalities will be graded per criteria in [Appendix C](#), but not considered in determining whether study stopping criteria have been met. On the other hand, abnormalities of VS that are either secondary to systemic or organ-specific clinical syndrome or primary disorders will be coded in the appropriate SOC (e.g., “cardiac disorders”, “respiratory disorders”, “immunological disorders”, etc.). These abnormalities will be considered in determining whether stopping criteria have been met.

Clinical AEs	Mild (Grade 1)	Moderate (Grade 2)	Severe (Grade 3)	Comments
CARDIOVASCULAR				
Arrhythmia		Asymptomatic or transient signs; no medical intervention required	Recurrent and/or persistent signs; symptomatic medical intervention required	
Hemorrhage	Estimated blood loss ≤100 mL	Estimated blood loss >100 mL; no transfusion required	Blood transfusion required	
RESPIRATORY				
Cough	Transient cough; no treatment required	Persistent cough; treatment required	Interferes with daily activities	
Bronchospasm, Acute	Transient bronchospasm; no treatment required; FEV1 71-80% of predicted peak flow	Requires treatment; normalizes with bronchodilator; FEV1 60-70% of predicted peak flow	No normalization with bronchodilator; FEV1 <60% of predicted peak flow	
Dyspnea	Does not interfere with usual and social activities	Interferes with usual and social activities; no treatment	Prevents usual and social activities OR requires treatment	
GASTROINTESTINAL				
Nausea	No interference with normal activity	Some interference with normal activity	Prevents daily activities	
Vomiting	No interference with activity OR 1-2 episodes in a 24-h period	Some interference with activity OR >2 episodes in a 24-h period	Prevents daily activity OR requires medical intervention	
Diarrhea	2-3 loose or watery stools in a 24-h period	4-5 loose OR watery stools in a 24-h period	6 or more loose or watery stools in a 24-h period OR requires IV hydration OR requires medical intervention	

Clinical AEs	Mild (Grade 1)	Moderate (Grade 2)	Severe (Grade 3)	Comments
Oral Discomfort / Dysphagia	Mild discomfort; no difficulty swallowing	Some limits on eating /drinking	Eating/talking very limited; unable to swallow solid foods	
LOCAL IV CATHETER REACTION				
IV site reaction	Not applicable	Erythema with associated symptoms (e.g., edema, pain, induration, phlebitis)	Ulceration or necrosis; severe tissue damage; operative intervention indicated	
SYSTEMIC REACTIONS				
Anaphylaxis **	--	--	Symptomatic bronchospasm, with or without urticaria; parenteral intervention indicated; allergy-related edema or angioedema; hypotension	
**Definition: A disorder characterized by an acute inflammatory reaction resulting from the release of histamine and histamine-like substances from mast cells, causing a hypersensitivity immune response. Clinically, it presents with breathing difficulty, dizziness, hypotension, cyanosis, and loss of consciousness, and may lead to death.				
Allergic Reaction	Pruritus without rash	Localized urticaria OR requires oral therapy	Generalized urticaria OR angioedema OR anaphylaxis OR requires epinephrine	
Hypersensitivity (including drug fever)	Transient flushing or rash; temperature 38.0-38.4°C (100.4-101.1°F)	Rash; flushing; urticaria; dyspnea; temperature 38.5 - 38.9°C (101.2 - 102.0°F)	Symptomatic bronchospasm with or without urticaria; parenteral medication indicated; allergy-related edema or angioedema; hypotension; temperature >38.9°C (>102.0°F)	

Clinical AEs	Mild (Grade 1)	Moderate (Grade 2)	Severe (Grade 3)	Comments
Headache	No interference with activity	Repeated use of non-narcotic pain reliever for more than 24 h OR some interference with activity	Significant; any use of narcotic pain reliever OR prevents daily activity OR requires triptans	
Fatigue	No interference with activity	Some interference with activity	Significant; prevents daily activity	
Myalgia	No interference with activity	Some interference with activity	Significant; prevents daily activity	
SKIN				
Mucocutaneous	Erythema, pruritus	Diffuse, maculopapular rash, dry desquamation	Vesiculation OR moist desquamation OR ulceration	
Pruritus	No or minimal interference with usual social and functional activities	Greater than minimal interference with usual social and functional activities	Inability to perform usual social and functional daily activities	
ALL OTHER CONDITIONS				
Illness or clinical AE (as defined according to applicable regulations)	Require minimal or no treatment; does not interfere with the subject's daily activities.	Result in a low level of inconvenience or concern with therapeutic measures; may cause some interference with functioning.	Interrupt a subject's usual daily activity and may require systemic drug therapy or other treatment; are usually incapacitating	

Table 8: Toxicity Grading Tables – Laboratory AEs

Laboratory AEs	Mild (Grade 1)	Moderate (Grade 2)	Severe (Grade 3)
Blood, serum, or plasma *			
Sodium decrease – mmol/L	130 - 131	125 –129	<125
Sodium increase – mmol/L	149 - 150	151 – 153	>153
Potassium increase – mmol/L	5.6 – 6.0	6.1 – 6.4	≥6.5
Potassium decrease – mmol/L	3.0 – 3.2	2.5 – 2.9	<2.5
Bicarbonate (CO ₂) increase – mmol/L	34 - 35	36 - 37	>37
Bicarbonate (CO ₂) decrease – mmol/L	17 - 18	14 - 16	<14
Glucose decrease, fasting – mg/dL	47 - 49	45 –46	<45
Glucose increase, fasting – mg/dL	116 – 125	126 – 249	≥250
Glucose increase, non-fasting – mg/dL	116 – 160	161 – 249	≥250
Blood urea nitrogen – mg/dL	25 - 27	28 – 32	>32
Creatinine increase, male – mg/dL	1.46 – 1.7	1.71 – 2.3	>2.3
Creatinine increase, female – mg/dL	1.21 – 1.5	1.51 – 2.0	>2.0
Calcium decrease – mg/dL	7.8 – 8.0	7.0 – 7.7	<7.0
Calcium increase – mg/dL	11.0 – 11.4	11.5 – 12.4	≥12.5
Total protein decrease – g/dL	5.1 – 5.7	4.6 – 5.0	<4.6
Albumin decrease – g/dL	2.8 – 3.4	2.5 – 2.7	<2.5
AST increase, male – U/L	46 – 115	116 – 220	>220
AST increase, female – U/L	36 - 90	91 - 175	>175
ALT increase, male – U/L	53 – 115	116 - 230	>230
ALT increase, female – U/L	39 – 95	96 – 190	>190
Alkaline phosphatase increase – U/L	151 – 240	241 – 360	>360
Total bilirubin (serum) increase – mg/dL (with other LFTs in the normal range)	1.5 – 2.0	2.1 – 2.5	>2.5
Total bilirubin (serum) increase – mg/dL (accompanied by a >3 x ULN increase in ALT or AST)**	1.5 – 1.7	1.8 – 2.1	>2.1
Hemoglobin decrease, female – g/dL	10.8 – 11.2	9.4 – 10.7	<9.4
Hemoglobin decrease, male – g/dL	11.8 – 12.9	10.0 – 11.7	<10.0
WBC increase – cells/μL	11,000 – 15,000	15,001 – 20,000	>20,000
WBC decrease – cells/μL	2,500 – 3,500	1,500 – 2,499	<1,500
Neutrophils decrease – cells/μL	1,200 – 1,499	1,000 – 1,199	<1,000
Lymphocytes decrease – cells/μL	750 – 849	500 – 749	<500

Laboratory AEs	Mild (Grade 1)	Moderate (Grade 2)	Severe (Grade 3)
Monocytes increase – cells/μL	1,101 – 2,000	2,001 – 3000	>3,000
Eosinophils increase – cells/μL	500 – 750	751 – 1,500	>1,500
Basophils increase – cells/μL	201 – 500	501 – 800	>800
Platelets decrease – cells/μL	120,000 – 124,000	100,000 – 119,000	<100,000
Urine*			
Protein	1+	2+	>2+
Glucose	1+	2+	>2+
Blood (dipstick)	1+	2+	>2+
Blood (microscopic) – RBCs per HPF	6-10	11-50	>50 and/or gross blood
WBC (microscopic) – WBC per HPF	6-10	11-50	>50
Bacteria (microscopic)	few	moderate	many

* Institutional normal reference ranges and allowable ranges at screening are provided in [Appendix B](#).

**ALT, males: >216 U/mL; ALT, females: >132 U/mL; AST, male or female: >126 U/mL)

Note 1: If a subject was accepted into the trial with a laboratory value of an analyte that overlaps with values used for grading Grade 1 laboratory abnormalities, an AE will be reported if the on-study value of the same analyte is different (worse) from the baseline.

Note 2: Safety laboratory results that are abnormal according to the local laboratory reference range, but not considered a Grade 1 abnormality, will be evaluated by the CTU clinician and reported as Grade 1 abnormalities if clinically significant. If not clinically significant, these will not be considered laboratory AEs and will thus not be graded but will be recorded in the source document and followed-up clinically at the discretion of the CTU clinician.

Note 3: Other laboratory parameters performed and reported as part of the CBC, metabolic panel, and UA will be evaluated by the study clinician, recorded in the source document, reported as laboratory AEs if clinically significant, and graded according to the criteria in [Section 9.2.1](#).

Note 4: If the dipstick UA is abnormal, a microscopic UA will be performed, and the results will supersede the results of the dipstick UA.

Note 5: Menstruating females with a positive dipstick UA or microscopic UA may be retested following cessation of menses.

Table 9: Toxicity Grading Tables – ECG

ECG interval abnormality	Grade 1	Grade 2	Grade 3
QTcF interval prolonged (msec)	Asymptomatic, QTcF 450-479 msec	Asymptomatic, QTcF 480-500 msec OR increase in interval 30-59 msec above baseline	Asymptomatic, QTcF >500 msec OR increase in interval ≥60 msec above baseline
PR interval prolonged (msec)	210-250 msec	>250 msec	Type II 2 nd degree AV block OR ventricular pause >3.0 sec

Note: Events will be coded as SAEs if there are life-threatening associated symptoms or signs (arrhythmia, CHF, hypotension, syncope, TdP, etc.)

Note: If a male subject was accepted into the trial with a QTcF value that overlaps with values used for grading Grade 1 QTcF prolongation, an AE will be reported if the QTcF value is higher than the baseline value

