- Review inclusion/exclusion criteria to confirm the subject remains eligible for enrollment
- Update MH (Day -1 in Period 1 only)
- Update Prior Medications
- Perform abbreviated PE (Perform on each check-in. In Period 1, do not perform only if the screening PE was completed ≤ 7 days from dosing.)
- Obtain VS
- Obtain weight
- Obtain blood and urine samples for clinical laboratory tests (collect on each check-in). In Period 1, do not collect if screening samples were collected ≤ 7 days from dosing.)
- For all women, a serum β -HCG pregnancy test will be done, and negative results confirmed before dosing
- Obtain urine sample for toxicology
- Perform urine alcohol test for alcohol use
- Obtain 12-lead standard ECG with 10-sec rhythm strip
- Counsel to avoid rigorous physical activity
- Review AEs/SAEs (Day -1 in Periods 2, 3, and 4, respectively, on study Days 8, 16, and 24)

Subjects who still meet the eligibility criteria on Day -1 before Period 1 will be admitted to the CTU on the same day.

For subsequent dosing periods (2, 3, and 4), subjects will be admitted on Day -1. Any new symptoms or abnormal assessments will be reviewed prior to dosing, and recorded as AEs.

Eligibility for continuation of dosing (dose 2, 3 and 4):

Dosing for subsequent periods may proceed if:

- A negative serum pregnancy test on Day -1 of each dosing period
- Females of childbearing potential and males still agree to use acceptable contraception for the duration of the trial and for 30 days (females) or 90 days (males) after Final Visit
- One of the following:
 - Subjects who did not experience any AE since the last dose administration
 - Any new or prior AEs were grade 1 or resolved, and in the opinion of the site principal investigator or appropriate sub-investigator, the AEs, individually or in cluster, do not pose a risk to the subject or would be likely to confound interpretation of the results.
 - Any new or prior AEs that were grade 2, should be either resolved or downgraded to Grade 1 and in the opinion of the site principal investigator or appropriate sub-investigator, the AEs, individually or in cluster do not pose a risk to the subject or would be likely to confound interpretation of the results.

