 - Any new or prior grade 3 AEs that were judged unrelated to study drug should be either resolved or downgraded to Grade 1 and in the opinion of the site principal investigator or appropriate sub-investigator, the AEs, individually or in cluster do not pose a risk to the subject or would be likely to confound interpretation of the results.

If a subject has a Grade 3 AE judged related to study drug administration, this subject will be withdrawn from the study and will not receive subsequent dosing. For all other AEs, dosing may be delayed up to 14 days in order to follow the AE for downgrading or resolution according to the above. If the subject does not meet the criteria for dosing specified above in 14 days, this subject will be withdrawn from the study and will not receive subsequent dosing.

After admission to the CTU, the subject will fast at least 8 h before dosing but will have access to water during that period.

7.4 Inpatient period (Days 1-2 in each dosing period) (Overall, Days 1-2, 9-10, 17-18, and 25-26 for dosing periods 1, 2, 3 and 4, respectively)

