9.5 Halting Rules

9.5.1 Study Halting Criteria

9.5.1.1 Halting Criteria for Zoliflodacin and Placebo Periods

Study dosing of zoliflodacin or placebo will be temporary halted, and a review of available safety data will be conducted by the SMC if any of the following occur after dosing:

1. Death of a subject following dosing regardless of relatedness to the study drug;
2. One subject with a non-fatal SAE that is considered related to the study drug by the study PI or authorized physician (listed in FDA Form 1572);
3. Two or more subjects experience a QTcF >500 msec or ≥ 60 msec above baseline, based on readings from at least two standard 12-lead ECGs after study drug administration;
4. Two or more subjects with a Grade 3 systemic AE coded in the same organ system that is considered related to the study drug by the study PI or authorized clinician;

Note: VS abnormalities will be considered part of a systemic disorder or an organ-specific condition, as described in Appendix C: Adverse Events Toxicity Grading Criteria

, in order to be included among the Study Halting Criteria.

5. One subject experiences a symptomatic ventricular tachyarrhythmia with or without QTcF prolongation after study drug administration;
6. An overall pattern of symptomatic, clinical non-serious events that may appear minor in terms of individual events, but that may collectively represent a serious potential safety concern and pose a risk to continuing a subject in the trial.

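### Protocol Table 7 and SAP Table 3 give a transient, asymptomatic, untreated ventricular tachyarrhythmia both Grade 3 and Grade 2, and if it is judged related the grade decides between mandatory withdrawal and possible further dosing

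*Protocol*

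**What the plan says.** Two rows of Protocol Table 7 (Appendix C) bear on a ventricular rhythm event.

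- Vital signs, Tachycardia, Grade 3: ">130 or ventricular dysrhythmias".
- Cardiovascular, Arrhythmia, Grade 2: "Asymptomatic or transient signs; no medical intervention required". Grade 3 in this row is "Recurrent and/or persistent signs; symptomatic medical intervention required".

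SAP Table 3 carries the same entries. On how the rows relate, Appendix C says only this: "Criteria are generally grouped by body system".

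Section 7.3 of the protocol ties later dosing to grade and relatedness.

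- Related Grade 3: "If a subject has a Grade 3 AE judged related to study drug administration, this subject will be withdrawn from the study". SAP Section 4.4.5 repeats this rule.
- Unrelated Grade 3: "Any new or prior grade 3 AEs that were judged unrelated to study drug should be either resolved or downgraded to Grade 1".
- Grade 2: "Any new or prior AEs that were grade 2, should be either resolved or downgraded to Grade 1".

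The last two also need the investigator's opinion on risk and confounding.

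For zoliflodacin and placebo periods, Section 9.5.1.1, criterion 4, halts dosing on this count, for events considered related: "Two or more subjects with a Grade 3 systemic AE coded in the same organ system". Section 9.5.1.2, criterion 3, sets the matching count at three subjects for moxifloxacin periods. Section 5.3.3 lists a ventricular tachyarrhythmia, with or without symptoms, among the reasons for which a subject may be removed after dosing.

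**The concern.** This trial studies QTcF because prolonged repolarization can lead to ventricular arrhythmia, so that event should have one grade. As written, a clinician who follows the tables literally can reach either of two grades for the same event, and each has a different consequence for the subject and for the halting count.

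There are also effects on the data. The severity breakdowns in SAP Tables 12 and 14 would depend on which row was used. Under the SAP's definition of tolerability (Section 3.3), an investigator withdrawal for an adverse event counts against zoliflodacin when it was the latest active treatment. The ECG SAP (Section 5.4) forms ΔΔQTcF within each subject as active minus placebo, so a subject withdrawn before the placebo period contributes no ΔΔQTcF.

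**Working it through.** No arithmetic decides this point, and the plan has no figure to reproduce. The check takes one event through the stated rules.

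**Test event.** A ventricular tachyarrhythmia after dosing, without symptoms or treatment, gone before the next check-in.

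**Step 1, Tachycardia row.** The ventricular entry is an alternative to the rate limit, not an addition to it, and the cell sets no condition on symptoms or treatment. Result: Grade 3.

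**Step 2, Arrhythmia row.** The Grade 2 cell is met. The Grade 3 cell is not, because the signs neither recur nor persist and no intervention is needed. Nothing limits the row to supraventricular rhythms. Result: Grade 2.

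**Step 3, tie-breakers.** None was found.
- The general severity scale in Appendix C applies only to abnormalities absent from the tables.
- Table 9 grades QTcF and PR prolongation; its only rhythm entry is in the PR row and does not cover ventricular tachyarrhythmia.
- The worst-severity rule in Section 11.4.3.1 concerns repeated occurrences of an adverse event.
- The highest-grade rule in Section 8.1.6 concerns repeat vital-sign measurements.

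**Step 4, consequences.**

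| Rule | Grade 3 (Tachycardia row) | Grade 2 (Arrhythmia row) |
|---|---|---|
| 7.3, judged related | Withdrawn, no further dosing | Dosing may proceed if resolved or downgraded and the investigator agrees |
| 7.3, judged unrelated | Dosing may proceed if resolved or downgraded and the investigator agrees | Same |
| 9.5.1.1 criterion 4, judged related | Counts toward two subjects | Does not count |
| 9.5.1.2 criterion 3, judged related | Counts toward three subjects | Does not count |

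**Step 5, other halting rules.** In 9.5.1.1, criterion 3 needs a QTcF threshold, criterion 5 needs symptoms, and criterion 6 concerns a pattern of symptomatic events. Section 9.5.1.2 has no ventricular criterion. For an asymptomatic event that is not serious and has no QTcF trigger, the Grade 3 count is the only explicit route to a halt.

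**Step 6, doses at stake.** A subject withdrawn after the dose in Period p loses 4 − p doses: 3, 2, 1 and 0 for Periods 1 to 4.

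**The case against.** The strongest reply is that the Tachycardia row is a heart-rate row. It is measured in bpm, and its Comments column asks for supine rest and at least three measurements with two concordant results. This has force. A reader might infer that any isolated ventricular finding on a tracing, such as a couplet, already has two grades. The documents do not support that, because a one-off finding does not plainly meet the row's comment. An asymptomatic ventricular tachycardia confirmed on repeat readings can still fit both rows. Whether the comment applies to a rhythm finding at all is not stated, and SAP Table 3 has no Comments column.

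A reader might also infer that the choice of row decides how the event is coded. It does not. The note under the vital-signs block of Table 7 sorts events by clinical nature: isolated, asymptomatic changes in a vital sign go to Investigations, and primary or organ-specific disorders go to their own organ class, whichever row supplied the grade. The halting difference comes from the grade alone.

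Section 5.3.3 addresses this event regardless of grade, so withdrawal is possible either way. That is correct, but the rule is discretionary and stands beside a mandatory one in 7.3. It adds a passage to reconcile. Nor is dosing after Grade 2 automatic, since it depends on resolution or downgrading and on the investigator's judgement.

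Last, this is a single-site trial with grading reviewed by the site investigator or designee, and SAP Table 16 lists moderate and severe events together. Both facts limit the reporting damage. Neither tells that reviewer which grade to assign.

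**Conclusion.** The contradiction stands, within limits. It concerns a transient, asymptomatic, untreated ventricular tachyarrhythmia; recurrent or persistent signs point to Grade 3 in the Arrhythmia row as well. The dosing and halting consequences differ only if the event is judged related to study drug.

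For one such event, the size is one mandatory withdrawal or none, up to three later doses given or not, and one count or none toward a halting threshold of two or three subjects. A reader might want a projected number of affected subjects. The documents give no rate for such events, so any projection would rest on an assumed rate. It would also need to leave out events judged unrelated and, for lost doses, events in Period 4.

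The point does not alter the primary QTcF decision rule. It is an inconsistency between stated rules, worth correcting because the grade drives action and the correction is cheap.

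**What to change.** The sponsor's medical team should reconcile the Tachycardia and Arrhythmia rows of Protocol Table 7, the same two rows of SAP Table 3, and Protocol Sections 5.3.3, 7.3 and 9.5.1, so that each ventricular event has one grade and one consistent consequence. The reconciled text should also say whether the repeat-measurement comment applies to rhythm findings. SAP Section 4.4.5, which repeats the withdrawal rule, should be kept in step.

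Editing either row alone would in effect choose a grade, so the choice should be made openly. This review does not say which grade or which dosing rule is right.

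The cost is a short wording change in each document, with no new data, procedures or analyses.
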